#### Page 56 of 99 Protocol No. CAIN457ADE16

Period	Screening Period	Treatment Period								Post-Treatment Follow-Up 						
Visit Name	Screening (Week -6 to Baseline)	Baseline	Week 1	Week 2	Week 3	Week 4	Week 8	Week 12	Week 16	Week 20	Week 24	Week 32	Week 40	Week 56	Week 68	USV 
Days	-42 to -1	1	8	15	22	29	57	85	113	141	169	225	281	393	477	
Randomization		Х														
Study drug administration		Х	Х	Х	Х	Х	Х	Х								

Confidential

X = assessment to be recorded in the clinical database or received electronically from a vendor.

S = source data.

1 = Ophthalmic examination (please refer to Section 8.3.4).

2 = For responders only. Non-responders and patients who relapse during follow-up, will receive a second treatment course (see next table).

3 = Unscheduled visits (USV) might be required e.g., if patients observe symptoms between scheduled visits or for safety reasons. The safety assessments listed herein may be performed at the discretion of the investigator as needed to resolve the reason for the unscheduled visit. (S)AE assessment and concomitant medications are mandatory for all unscheduled visits.

4 = Kits for urinalysis will be provided by central lab and test is performed locally.

6 = Gorman score/subjective diplopia score (Bahn et al 1987).

() = Parentheses denote assessments that are on a per need basis at investigator's discretion.

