# 10.2 Additional Safety Monitoring

#### 10.2.1 Liver safety monitoring

To ensure patient safety and enhance reliability in determining the hepatotoxic potential of an investigational drug and/or concomitant medication (e.g., thyrostatic treatment) and/or hyperthyroidism related liver enzyme elevation, a standardized process for identification, monitoring and evaluation of liver events has to be followed.

The following 2 categories of abnormalities / AEs have to be considered during the course of the study (irrespective of whether classified/reported as (S)AE):

- Liver laboratory triggers, which will require repeated assessments of the abnormal laboratory parameter
- Liver events, which will require close observation, follow-up monitoring and completion of the standard base Liver CRF pages

Every liver laboratory trigger or liver event should be followed up by the investigator or designated personnel at the trial site as summarized below (please see Appendix 2 for detailed information).

For the liver laboratory trigger:

• Repeating the liver function test (LFT) within the next week to confirm elevation.

These LFT repeats must be performed using the central laboratory if possible. If this is not possible, then the repeats can be performed at a local laboratory to monitor the safety of the patient. Repeats laboratory must then be performed at central laboratory as soon as possible. If a liver event is subsequently reported, any local LFTs previously conducted that are associated with this event must be reported on the Liver CRF pages.

• If the elevation is confirmed, close observation of the patient will be initiated, including consideration of treatment interruption if deemed appropriate.

For the liver events:

- Repeating the LFT to confirm elevation as appropriate
- Discontinuation of the investigational drug if appropriate
- Hospitalization of the patient if appropriate
- A causality assessment of the liver event via exclusion of alternative causes (e.g., disease, co-medications)
- An investigation of the liver event, which needs to be followed until resolution

These investigations can include serology tests, imaging and pathology assessments, hepatologist consultancies, based on the investigator's discretion. All follow-up information, and the procedures performed must be recorded on appropriate CRF pages, including the liver event overview CRF pages.

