2.1.1.2 Visit and analysis window

Since the actual visit for a subject may not exactly coincide with their targeted visit date, the actual visit date is mapped to a study visit.

The nearest study day window will be utilized to define study visit for laboratory, vital signs, number of doses received, ophthalmological assessments and GO-QoL collected during office visits before dose is administered.

In case of multiple assessments within an analysis window, the day the closest to the scheduled visit day will be used.

Unscheduled visits will only be used when there is no measurement from the scheduled visit in the defined window. In case of multiple assessment values among the same type of visit (i.e., scheduled vs. unscheduled) within the same analysis window, the closest to the scheduled visit

day will be used. In case of equal distances (e.g., same day), the latest assessment value will be used.

For assessments that are not scheduled at all visits (e.g. hematology assessments) the derivation formula is:

- Lower limit = upper limit of previous visit +1.
- Upper limit = integer value of (target day + target day of next visit)/2.

Table 2-1 Study visit windows during DBTP

Study visit	Target day	Study day
DBTP		
Baseline	1	≤1
Week 1	8	2 – 11
Week 2	15	12 – 18
Week 3	22	19 – 25
Week 4	29	26 – 43
Week 8	57	44 – 71
Week 12	85	72 – 99
Week 16	113	100 – 127

Table 2-2 Study visit windows during open-label treatment and follow-up for non-responders

Study visit	Target day	Study day
Week NR 16*	113	100 – 116
Week NR 17	120	117 – 123
Week NR 18	127	124 – 130
Week NR 19	134	131 – 137
Week NR 20	141	138 – 155
Week NR 24	169	156 – 183
Week NR 28	197	184 – 211
Week NR 32	225	212 – 253
Week NR 40	281	254 – 337
Week NR 56	393	338 – 448

*Only applicable for assessments that have not been performed at Week 16 visit in non-responders.

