2.8.3 Laboratory data

All laboratory data (hematology, clinical chemistry, urinalysis and thyroid-related parameters) from the on-treatment period will be listed by treatment group, patient, and visit/time and if normal ranges are available abnormalities will be flagged. Summary statistics for clinical notable laboratory values will be provided by treatment and visit.

The following clinical notable laboratory values are defined:

Liver function and related variables	
ALT (SGPT)	> 3 × ULN
AST (SGOT)	> 3 × ULN
Total bilirubin	> 2 × ULN
Alkaline phosphatase	> 2 × ULN
Renal function and electrolyte variables	
Creatinine (serum):	> 1.5 × ULN
Hematology variables	
Hemoglobin	≥ 20 g/dL decrease from Baseline
Platelet count	< LLN
White blood cell count:	< 0.8 × LLN
Neutrophils	< 0.9 × LLN
Eosinophils	> 1.1 × ULN
Lymphocytes	> 1.1 × ULN
Urinalysis variables	
Protein urine dipstick	++* (* ++ is ≥ 100 mg/dL)

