2.8.4.2 Vital signs

Notable vital signs abnormalities will be analyzed by treatment group for the DBTP and the entire study period. A frequency table will be provided.

Normal blood pressure will be defined as systolic blood pressure (SBP) of 90 to < 120 mmHg, and diastolic blood pressure of 60 to < 80 mmHg under the measurement conditions outlined in the protocol. Notable blood pressure findings will be hypertension (SBP of ≥ 140 mmHg and/or diastolic blood pressure [DBP] of ≥ 90 mmHg) or hypotension (SBP of < 90 mmHg and/or a DBP of < 60 mmHg).

A normal pulse rate will be defined as a rate of 60 to 100 beats per minute (bpm). Notable pulse rate abnormality will be a rate below 60 bpm (bradycardia) or above 100 bpm (tachycardia).

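### The SAP's visit-window rule prefers scheduled values even for safety outputs, so notable laboratory abnormalities seen only at unscheduled visits can go uncounted

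*SAP*

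**What the plan says.** SAP 2.1.1.2 sets one windowing scheme and names safety data in its scope: "The nearest study day window will be utilized to define study visit for laboratory, vital signs". Two selection rules follow. The first gives priority to scheduled visits: "Unscheduled visits will only be used when there is no measurement from the scheduled visit in the defined window". The second picks by distance from the target day: "In case of multiple assessments within an analysis window, the day the closest to the scheduled visit day will be used". Neither selects the worst value. For assessments not made at every visit, the window boundary is "Upper limit = integer value of (target day + target day of next visit)/2".

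The safety outputs are specified as follows:

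- **Laboratory (SAP 2.8.3):** "Summary statistics for clinical notable laboratory values will be provided by treatment and visit". All on-treatment laboratory data are also listed, with abnormal values flagged where normal ranges exist.
- **Vital signs (SAP 2.8.4.2):** "Notable vital signs abnormalities will be analyzed by treatment group for the DBTP and the entire study period", as a frequency table.
- **Table 2-4:** crude incidence of notable vital signs and laboratory criteria, for Day 1 to Week 16 and for the whole study.

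None of these has a worst-value or any-value rule. The other places where one could sit, SAP 5.3 (laboratory derivations) and 5.6 (calculation rules), are marked not applicable.

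The protocol expects off-schedule measurements. Footnote 3 of Table 8-1 says "Unscheduled visits (USV) might be required e.g., if patients observe symptoms between scheduled visits or for safety reasons", and the table allows laboratory tests and vital signs at such visits. For a liver laboratory trigger, Protocol 10.2.1 requires "Repeating the liver function test (LFT) within the next week to confirm elevation". Protocol Table 16-4 shortens this to 48 hours for several larger elevations.

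**The concern.** Unscheduled visits are held because of symptoms or a safety question, so their results are more likely than routine ones to be abnormal. A rule that puts the routine value first suits a mean-by-visit summary. Applied to a count of patients with an abnormality, it can only lower that count.

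Protocol 4.5 names neutropenia as an observed risk, describes the cases as generally transient, and says that patients on anti-thyroid medication may be at higher risk. A transient fall is the kind of finding that may be present at an extra visit and gone by the next scheduled one. The notable-value output is the only laboratory summary the SAP specifies, so an undercount there has no second laboratory table to correct it.

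**Working it through.** **1. Reproduce the windows.** Target days are 29, 57, 85 and 113 (Weeks 4, 8, 12, 16), then 141 (Week 20 or NR20). The upper limit is the integer part of (target + next target)/2:

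- Week 4: (29 + 57)/2 = 43
- Week 8: (57 + 85)/2 = 71
- Week 12: (85 + 113)/2 = 99
- Week 16: (113 + 141)/2 = 127

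These match SAP Table 2-1. Chemistry and hematology are not scheduled at Weeks 1 to 3 (Protocol Table 8-1). Their Week 4 window therefore starts the day after the Baseline window closes on Day 1, and runs over Days 2 to 43, which is 42 days. The next windows are 44–71, 72–99 and 100–127, 28 days each. No day from 2 to 127 lies outside a window.

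**2. Where a required repeat falls.** Add 7 days, the longer repeat interval, to an on-target scheduled laboratory visit: 29 + 7 = 36 (limit 43), 57 + 7 = 64 (71), 85 + 7 = 92 (99), 113 + 7 = 120 (127). The same holds in the open-label course: 141 + 7 = 148 (155), 169 + 7 = 176 (183), 197 + 7 = 204 (211), 225 + 7 = 232 (253). The repeat always shares the window of the scheduled value and is not selected.

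**3. Does that change the count?** Compare the repeat triggers (Protocol Tables 16-3 and 16-4) with the notable limits (SAP 2.8.3):

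| Scheduled value triggering a repeat | Notable limit | Already counted? |
|---|---|---|
| ALT or AST > 3 × ULN | > 3 × ULN | Yes |
| ALP > 2 × ULN | > 2 × ULN | Yes |
| Total bilirubin > 2 × ULN | > 2 × ULN | Yes |
| Total bilirubin > 1.5 to ≤ 2 × ULN | > 2 × ULN | No |

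The count uses a threshold and does not grade the peak. A patient triggered at a scheduled visit in the first three rows is counted whatever the repeat shows. A notable value can be lost in three situations:

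- bilirubin of 1.5–2 × ULN rises above 2 × ULN on repeat;
- a different parameter crosses its limit on the repeat panel;
- the abnormality was first found at an unscheduled visit.

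**4. Apply the rule to constructed patients.** The values are invented for illustration and given in × ULN; S = scheduled, U = unscheduled.

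| Values | Notable by the window rule | Notable using all values |
|---|---|---|
| ALT: Day 29 S 1.0, Day 36 U 6.0, Day 57 S 1.2 | No | Yes |
| ALT: Day 10 U 5.0, Day 29 S 1.1 | No | Yes |
| Bilirubin: Day 29 S 1.8, Day 35 U 2.6, Day 57 S 1.0 | No | Yes |
| ALT: Day 29 S 4.0, Day 35 U 6.0, Day 57 S 1.2 | Yes | Yes |
| ALT: Day 29 S 1.0, Day 60 U 5.0 (Week 8 missing), Day 85 S 1.0 | Yes | Yes |

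**5. Size of one missed patient.** The SAP gives 28 randomized. The split by arm is not given; 14 per arm is an assumption from 1:1 allocation. One patient is 1/14 = 7.1 percentage points. For arms of 12 to 16 it is 1/12 = 8.3 down to 1/16 = 6.3 points. With the continuity-corrected score interval, 0/14 has a 95% CI of 0 to 26.8%, and 1/14 has 0.4% to about 36%.

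**The case against.** The strongest defence has four parts.

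- **Scope.** SAP 2.1.1.2 is a visit-mapping rule. The vital-sign table and Table 2-4 are by period, SAP 5.4.3 defines crude incidence simply as subjects with the event over n, and SAP 2.1 defers output details to table shells that are not part of these documents. This stands: a reader might infer that unscheduled peaks are excluded from every notable-abnormality table, but for the period-level outputs the SAP is silent. The general rule would exclude them by default, and nothing says that it was meant to.
- **Liver repeats.** A reader might also infer that the required repeats systematically vanish from the counts. Step 3 shows that for most triggers the repeat makes no difference.
- **Other routes.** Laboratory values stay in the flagged listing. Clinically significant abnormalities must be recorded as medical history or adverse events (Protocol 8.4.1), and treatment-emergent events are tabulated by class, term and severity (SAP 2.8.1). This stands too: the documents do not support a reading that the data are lost or that a serious signal would be hidden. It does not make the notable count correct, since an off-schedule value can pass a notable limit without being judged clinically significant. For vital signs, the SAP section specifies no listing, although Protocol 12.5.2 does.
- **Materiality.** The trial stopped with 28 patients, the analysis is descriptive, and the rule is the same in both arms. No bias between arms is shown. That limits the weight of the point, but the table would still understate what was observed.

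The gap-free coverage is also shown only to Day 127. Chemistry and hematology are not scheduled for responders after Week 24 or at NR56, so a late unscheduled result may have no scheduled competitor.

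**Conclusion.** The point holds for the by-visit notable laboratory table. Up to Day 127, an abnormal chemistry or hematology value seen only at an unscheduled visit is not counted if the patient has a scheduled value in the same window. For notable vital signs and the period-level incidence in Table 2-4, the defect is an unstated choice of input values, which the programmer would have to settle.

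The consequence is possible undercounting in summary tables, by 7.1 percentage points per missed patient under the assumed 14 per arm. That figure is the weight of one patient and does not estimate how many would be missed; the documents give no basis for such an estimate. The conclusion also assumes that repeat tests are recorded as unscheduled visits and that the table shells contain no contrary rule. It is worth correcting because this is the SAP's only specified laboratory summary.

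**What to change.** In SAP 2.1.1.2, limit the scheduled-over-unscheduled and closest-to-target rules to by-visit descriptive summaries. In SAP 2.8.3, 2.8.4.2 and Table 2-4, state that crude incidence of notable laboratory and vital-sign values uses all post-first-dose values in the analysis period, scheduled and unscheduled, and that each patient is counted once per criterion. If the by-visit layout in 2.8.3 is kept, show the per-period count beside it.

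The cost is a few SAP sentences and a small programming change. No new data are needed.

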### Follow-up/open-label retreatment period (Week 16 up to Week 108)

• Proptosis non-responders at Week 16 (as defined in Section 3) will be offered the option of open-label secukinumab treatment (with maintenance of blind of initial randomized treatment) for a duration of 16 weeks, i.e., up to Week 32 with last dose at Week 28, as follows:

Open-label secukinumab 300 mg s.c. at Week 16, 17, 18, 19, 20, 24 and 28. Thereafter (i.e., from Week 32), patients will be followed up for a further 24 weeks to safety.

• Proptosis relapsers (as defined in Section 3) from Week 16 to Week 68 will be offered the option of retreatment with open-label secukinumab for a duration of 16 weeks (with maintenance of blind to initial randomized treatment) at the time of relapse as follows: Open-label secukinumab 300 mg s.c. at time of relapse, then at 1, 2, 3, 4, 8 and 12 weeks since time of relapse. Thereafter, patients will be followed up for a further 24 weeks (i.e., 40 weeks after start of retreatment) to assess

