### Premature discontinuation of study

Participants who prematurely discontinue the study for any reason should be scheduled for a visit as soon as possible, at which time all of the assessments listed for the study discontinuation visit will be performed. This study discontinuation visit should include all assessments of the Week 16 (if discontinued during double-blind treatment), NR32 (for non-responders), R16 (for relapsers) or Week 68 (for patients who discontinued during the follow-up period) visit.

Additionally, all randomized and/or treated patients should have a follow-up (EOS) visit conducted 12 weeks after last administration of study treatment, if not yet completed (or at least a safety follow-up call or contact, if a visit cannot be performed). This EOS visit includes all assessments of the Week 24 (if discontinued during the double-blind treatment period or the follow-up for responders), Week NR40 (for non-responders) or Week R24 (for relapsers) visit. The information collected is recorded in the eCRF. Documentation of attempts to contact the patient should be recorded in the source documentation.

For all premature discontinuations noted above, if the patient fails to return for these assessments for unknown reasons, every effort (e.g., telephone, e-mail, letter) should be made to contact the participant/pre-designated contact as specified in the lost to follow-up section. This contact should preferably be done according to the study visit schedule.

If the patient cannot or is unwilling to attend any visit(s), the site staff should maintain regular telephone contact with the patient, or with a person pre-designated by the patient. This telephone contact should preferably be done according to the study visit schedule.

After study treatment discontinuation or study discontinuation, at a minimum, in abbreviated visits, the following data should be collected at clinic visits or via telephone/email contact:

- New/concomitant treatments
- AEs/SAEs

The investigator must also contact the IRT to register the patient's discontinuation from study treatment.

If discontinuation occurs because treatment code has been broken, please refer to Emergency breaking of treatment code section.

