#### **Clinical laboratory evaluations**

All laboratory data will be listed by treatment group, patient, and visit/time and if normal ranges are available abnormalities will be flagged. Summary statistics will be provided by treatment and visit/time.

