2.8 Safety analyses

Summaries may be performed separately for initial (Baseline to Week 16) period and entire study period (including follow-up). Week 16 is chosen due to the fact that patients may be switched to another treatment at this time. Use of data up to and including the last visit before first switch opportunity provides an unbiased comparison between AIN and placebo; data collected beyond Week 16 are included in analyses which summarize the entire study period.

All listings and tables will be presented by treatment group. Safety summaries include only data from the on-treatment period and follow-up period with the exception of Baseline data that will also be summarized where appropriate (e.g., change from Baseline summaries). The on-treatment period is defined as date of first treatment to (date of last treatment + 84 days).

In addition, a separate summary for death including on-treatment and post-treatment deaths will be provided.

In particular, summary tables for AEs will summarize only on-treatment events, with a start date during the on-treatment period (treatment-emergent AEs) for the DBTP and the entire study period.

Missing data will not be imputed for safety endpoints.

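### The SAP's laboratory listing stops at last dose + 84 days, the nominal day of the 12-week post-dose visit, so late final bloods and the Week NR56 thyroid panel go unlisted

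*SAP*

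**What the plan says.** **Listing rule.** SAP 2.8.3 (Laboratory data) covers hematology, chemistry, urinalysis and thyroid parameters. Data "from the on-treatment period will be listed by treatment group, patient, and visit/time", with out-of-range values flagged. The only laboratory summary planned there is of notable values, by treatment and visit.

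**Cut-off.** SAP 2.8: "The on-treatment period is defined as date of first treatment to (date of last treatment + 84 days"). No visit tolerance is attached. The same section says that safety summaries draw on both the on-treatment and the follow-up period, and Table 2-4 plans crude incidence of notable laboratory values for the entire study phase.

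**Dosing and visits.** For non-responders the protocol plans "Open-label secukinumab 300 mg s.c. at Week 16, 17, 18, 19, 20, 24 and 28". SAP Table 2-2 gives the last-dose visit as "Week NR 28 197 184 – 211" and the next-but-one visit as "Week NR 40 281 254 – 337". Protocol Table 8-2 schedules the last hematology and chemistry at NR40, and thyroid tests at both NR40 and NR56. For patients who leave the study early, the protocol wants an end-of-study visit "conducted 12 weeks after last administration of study treatment, if not yet completed".

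**Protocol listing rule.** Protocol 12.5.2 (Clinical laboratory evaluations): "All laboratory data will be listed by treatment group, patient, and visit/time". It sets no period limit. The restriction earlier in 12.5.2 concerns tables and figures, and it includes follow-up.

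**Declared changes.** SAP Section 4 names only the move to descriptive efficacy analysis and the dropping of exploratory endpoints.

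**The concern.** The visit meant to capture safety 12 weeks after the last dose falls, by design, on the last day that the listing accepts. A patient bled on the target day is listed; the same patient bled a day later is not. The SAP itself recognises in 2.1.1.2 that actual visits will not always coincide with target dates.

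There are two consequences. First, a notable value drawn after the cut-off can be counted in a table that covers follow-up, yet be absent from the listing a reader would use to find the patient and the value. Second, thyroid parameters have no notable-value threshold in SAP 2.8.3, so the listing is their only planned output, and the NR56 thyroid results fall outside it. With 28 patients randomized and all analyses descriptive, patient-level listings carry much of the safety information.

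**Working it through.** **Inputs**
- Cut-off: last dose + 84 days (SAP 2.8), and 12 weeks × 7 = 84 days.
- Last planned doses: NR28, Day 197 (SAP Table 2-2); Week 12, Day 85 (SAP Table 2-1).
- Target days: NR40 = 281 and NR56 = 393 (SAP Table 2-2); Week 24 = 169 (Protocol Table 8-1).

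**1. Reproduce the plan's own window.** The SAP rule is "Upper limit = integer value of (target day + target day of next visit)/2". For NR40, (281 + 393)/2 = 337, as printed. For NR28, (197 + 225)/2 = 211, as printed. All nine upper limits from NR16 to NR40 that the rule defines reproduce exactly, so Table 2-2 is internally consistent.

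**2. Locate the cut-off with on-time dosing.**
- Open-label course: 197 + 84 = 281 = NR40 target.
- Blinded course only: 85 + 84 = 169 = Week 24 target. For non-responders who decline open-label treatment, the end-of-study visit is set 8 weeks after Week 16: 113 + 56 = 169, the same day.
- Early stoppers: the visit is due 12 weeks after the last dose, which is the cut-off by definition.

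A draw on Day 281 is listed and a draw on Day 282 is not, although 282 still maps to NR40.

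**3. Let the last dose move.** The clock runs from the actual dose. Across the NR28 window (Days 184 to 211) the cut-off runs from 184 + 84 = 268 to 211 + 84 = 295. After a dose on Day 196 or earlier (196 + 84 = 280), even an NR40 sample taken exactly on Day 281 is unlisted. After a late dose the NR40 visit gains some slack.

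**4. NR56 thyroid panel.** 393 − 197 = 196 days after an on-time last dose, or 393 − 281 = 112 days past the cut-off. Even with a last dose on Day 211, 393 − 295 = 98 days past it.

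**5. Where a sample beyond 84 days can still appear**

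| Result | Listing (2.8.3) | Notable-value tables (2.8.3, Table 2-4) | AE listing (2.8.1) |
|---|---|---|---|
| Notable value | no | yes, if follow-up is included as 2.8 says | only if clinically significant |
| Non-notable hematology or chemistry | no | no | only if clinically significant |
| Thyroid value | no | no (no threshold defined) | only if clinically significant |

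**The case against.** The 84-day limit is a coherent convention. It also defines the end-of-treatment date (SAP 2.1.1.1), treatment-emergent events and exposure (2.1.1.5) and censoring for incidence rates (5.4.3). That is a good reason to keep the definition. It does not explain why a listing, which estimates nothing, should be cut by it when the protocol lists everything.

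The effect is also limited. Protocol 8.4.1 requires clinically significant abnormalities to be recorded as medical history or adverse events, and SAP 2.8.1 lists all adverse events. Protocol Section 8 asks sites to keep visits as near the planned day as they can. The study was terminated and is purely descriptive, so no estimate, test or planned summary count changes. All of this stands, and it sets the size of the point.

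Stronger readings that a reader might infer, and why they fail:
- **Table 2-2 is wrong, or Day 337 is the tolerance for the final hematology and chemistry.** The table follows its own rule. Day 337 is derived from the NR56 target, and hematology and chemistry are not scheduled at NR56, so the rule for assessments not done at every visit gives them no upper limit at NR40. Day 337 applies directly to thyroid bloods.
- **Two thirds of NR40 results are lost.** With on-time dosing, 337 − 281 = 56 of the 337 − 254 + 1 = 84 window days (67%) lie after the cut-off. That counts calendar days, not visits or patients, and the documents give no distribution of visit dates.
- **Late abnormalities disappear from the report.** Only the listed value goes; the tables and the AE listing can still carry the finding.
- **Late thyroid status is a required analysis.** Inclusion criterion 6 asks for every effort to keep patients euthyroid to the end of the study. That makes the values of interest, but it is not an analysis objective.

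**Conclusion.** The point holds as a mismatch in the scope of a listing. The defect lies in SAP 2.8 and 2.8.3 read together: followed as written, they exclude any laboratory sample taken more than 84 days after the actual last dose. They place that limit on the nominal day of the last scheduled hematology and chemistry, and they exclude the NR56 thyroid panel. This departs from Protocol 12.5.2 without a declaration in SAP Section 4, and it allows a table and the listing behind it to disagree.

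What is lost from every planned output is the set of late thyroid and non-notable values, apart from any that are reported as adverse events. The number of patients is unknown. The 23 who had entered follow-up at termination (SAP Section 1) are a ceiling, because the documents do not say how many reached NR40 or NR56, or how many attended late. The Day 281 and Day 169 figures assume on-time last doses; with other dosing dates the limit moves as shown.

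The point is worth correcting before the listings are produced, mainly because the correction is almost free. It does not bear on the efficacy conclusions.

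**What to change.** - In SAP 2.8.3, list all laboratory data through end of study and flag each record as on-treatment (up to last dose + 84 days) or post-treatment. SAP 2.8.2 already handles deaths in this way. The 84-day definition itself stays as it is.
- If the restriction is intended, state it in SAP Section 4 as a change from Protocol 12.5.2 and give the reason.
- Add one sentence to SAP 2.8.3 confirming that the notable-value tables include follow-up results, in line with SAP 2.8 and Table 2-4.
- Leave Table 2-2 unchanged.

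Cost: a few sentences in the SAP, one derived flag and a longer listing. No new data are needed.
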